9.1.3 Study Unblinding

After database lock, the responsible statistician will request the treatment codes, the study will be unblinded, and the statistical analysis will be conducted.

10. SAFETY AND ADVERSE EVENTS

10.1 Potential Risks and Benefits

At screening, we will collect standardized historical, symptomatic, physical exam, and laboratory parameters to identify health conditions that represent risks for participation in the study's procedures.

10.1.1 Potential Risks

Nicotinamide Riboside: Nicotinamide riboside is well-tolerated in patients, with few adverse events reported in a minority (3.3%) of patients¹⁶:

- Mild nausea
- Mild skin rash
- Mild flushing/hot flashes
- Mild leg cramps
- Increased bruising

None of the reported adverse events led to discontinuation of NR during its intervention period.

Phlebotomy: The risks associated with having blood drawn, including the dried blood spot from the finger prick, include bruising and local discomfort. Rarely an infection may occur at this site, and if an infection does occur it will be treated by the study physician.

Magnetic Resonance Imaging: MRI is a safe procedure for subjects who do not have metal implants or other contraindications. Individuals who have electrically, magnetically, or mechanically-activated implants (such as

Randomized, Placebo-Controlled Parallel Group Clinical Trial of Nicotinamide Riboside to evaluate NAD+ Levels in Individuals with Persistent Cognitive and Physical Symptoms After COVID19 Illness ("Long-COVID")

Version 1.1

heart pacemakers) or those who have clips on blood vessels in their brain will not be allowed to participate in the study due to risks associated with MRI scanning. The MRI will be operated in a manner accepted by the FDA. The protocol requires subjects to remain still within a relatively confined space during the scanning session, and the scanner makes loud knocking and beeping sounds as it takes images. While subjects with severe claustrophobia are excluded from the study, some subjects may find the physical confinement or noise uncomfortable. Every effort will be made to enhance each subject's comfort level, and subjects will be given earplugs to reduce discomfort due to noise. If a subject notices any discomfort while in the MRI scanner, (s)he should notify the administrator immediately. If the discomfort cannot be stopped, the scanning session will be stopped. The MRI has the potential, during normal routine use, to cause localized warming of the skin and underlying tissues. Subjects should immediately inform the study staff if they experience discomfort due to warming of the skin and the procedure will be stopped.

Neurocognitive testing: The neurocognitive tests that will be administered to assess mental performance may be stressful and potentially cause anxiety, fatigue, and frustration. In our prior experience with similar protocols, risks have occurred infrequently and very few subjects have terminated testing. However, testing will be discontinued immediately upon any request by the subject to do so. With the evaluation of individuals with cognitive complaints, there is always the potential for a subject to enter the study with subjective cognitive concerns and subsequently demonstrate a decline in cognitive performance throughout the course of the study to a level consistent with a diagnosis of mild cognitive impairment (MCI). If this occurs, a licensed clinician will meet with the subject and suggest that they see their primary care provider for further evaluation.

Questionnaires: Questionnaires administered during the protocol may cause subjects to feel sad or upset about how residual symptoms of COVID-19 are affecting their quality of life. Study staff is experienced with such evaluations and sensitive to these issues. Any question can be omitted per the subject's request.

Wrist Actigraphy: The wrist actigraph, the Fitbit Charge 4, may cause some minor discomfort due to prolonged wearing, but the risk of such discomfort will be minimized by ensuring the wristband fits the subject properly (e.g. is not too tight or does not cause irritation). If the subject does experience discomfort, another wristband will be ordered to try to eliminate the discomfort.

SARS-CoV-2 negative (PCR): The nasal swab that is required for this test may cause some discomfort or, in rare occasions, slight pain.

Videoconferencing: Visits that take place via videoconferencing may allow research staff to learn more about the subject's home and cohabitants than an office visit. The study team will use a secure Zoom videoconferencing platform and conduct the visit in a private location to ensure personal information about the subject is kept confidential.

Other Risks: Reviewing health-related information might be stressful or make the subject feel uncomfortable. Subjects do not have to answer any questions they do not want to. In addition, there may be incidental medical findings as a result of the physical examination. The BDI inquires about suicidality. After the subject completes this instrument during the study visit, the coordinator will review the subjects' answers to these questions. A response of 2 or 3 on Question 9 of the BDI, or any spontaneous expression of suicidality will result in emergent evaluation by a licensed clinician member of study staff for appropriate assessment and triage. If a participant provides a response of "1", it will be considered non-urgent and a licensed clinician member of the

Randomized, Placebo-Controlled Parallel Group Clinical Trial of Nicotinamide Riboside to evaluate NAD+ Levels in Individuals with Persistent Cognitive and Physical Symptoms After COVID19 Illness ("Long-COVID")

Version 1.1

study staff will conduct an appropriate assessment and triage of the participant if necessary either in person, on the phone or virtually via the Zoom platform within 48 hours of being notified.

10.1.2 Known Potential Benefits

NR has been tested in a number of clinical trials in middle-aged and elderly patients and has shown to be well-tolerated. If successful, this trial will further understand of the effects of NR on NAD+ levels, as well as of standard and personalized assessment of cognitive, neuropsychiatric, physical and everyday functioning, in individuals who were infected with COVID-19 and are currently experiencing residual and persisting symptoms. This trial is also assessing multiple biomarkers in concert with clinical outcomes, which will provide a detailed understanding of NR activity and provide a well-curated data set for the community of individuals who had COVID-19 to improve our understanding of the long-term effects of COVID-19.

10.2 Data Security

10.2.1 Laptop Computer

Subjects will be provided a study-laptop during the visit to complete self-reported measures (i.e., BDI, BAI, PCL-C, ECog, BRIEF-A, PSQI, IPAQ, Fatigue Severity Scale) on REDCap and the online Continuous Performance Test (CPT). The laptop will be used only to complete the questionnaires on REDCap and the CPT. A study coordinator will always be present to address questions. No PHI or personally identifiable information will be entered into the system, so there are no additional data safety risks to the subject. The study laptop will be registered under the Principal Investigator and no identifying information will be required to sign in. There will be a password that will be available to the Principal Investigator and study coordinators, and not the participants. The computer has been encrypted using Bitlocker, per MGB's policies.

10.2.2 Mobile device

Fitbit is a web-based application that require no PHI or personally identifiable information be entered into the system, so there are no additional data safety risks to the subject if they use their personal mobile device, tablet or computers. Subjects will sync Fitbit activity tracking through the Fitbit app downloaded to their personal mobile device, tablet or computers by logging into the application with their provided, deidentified account.

10.2.3 Fitbit activity tracker

A study coordinator will create a unique, deidentified email and password combination to create an account on Fitbit.com. To create an account, the following information will be required: first and last Name (a de-identified placeholder name], date of birth (January 01, year of birth), gender, height, and weight. The subject will be given the associated account information so that they are able to login, sync their device, and use the Fitbit dashboard. The subject will be notified that the researcher will also have full access to their account and will be able to freely view and download the subject's data for research purposes. A copy of Fitbit's Privacy Policy and Terms of Service will also be reviewed by the subject during the consenting process. By consenting to the study, the subject is also agreeing to these policies and terms. ⁴¹

After the subject has completed or if they are withdrawn from the study, their Fitbit account and all associated data will be deleted. However, prior to deleting the account, the de-identified study data will be downloaded and stored confidentially on Partner's computers for study purposes.

11. MONITORING AND QUALITY ASSURANCE

Randomized, Placebo-Controlled Parallel Group Clinical Trial of Nicotinamide Riboside to evaluate NAD+ Levels in Individuals with Persistent Cognitive and Physical Symptoms After COVID19 Illness ("Long-COVID")

Version 1.1

The adverse event (AE) definitions and reporting procedures provided in this protocol comply with all applicable United States Food and Drug Administration (FDA) regulations and International Conference on Harmonisation (ICH) guidelines. The PI will carefully monitor each subject throughout the study for possible adverse events. All AEs will be documented on CRFs designed specifically for this purpose. It will be important to report all AEs, whether serious or non-serious.

11.1 Independent Monitoring of Source Data

The PI will ultimately be responsible for the validity and integrity of the data collected at the MGH site, and for ensuring that the study is conducted in accordance with the IRB-approved protocol. After data is collected and recorded on forms, the study coordinator may input the data into the REDCap database. Entries will be reviewed for accuracy and completeness by a second study coordinator. Study coordinators will also review the subjects' responses on REDcap to ensure that no data is missing. Finally, the PI or their designee (Co-I) will conduct monthly reviews to check that data in REDCap accurately reflects the data collected on the original data capture forms. The research team (PI, Co-I, research coordinators) will subsequently meet to discuss the results of this review, as well as case report forms and source documentation.

All electronic documentation will be stored on password-protected devices in locked cabinets located in secured areas. Paper forms will be stored in locked cabinets located in secured areas.

11.2 Safety Monitoring

The adverse event (AE) definitions and reporting procedures provided in this protocol comply with all applicable United States Food and Drug Administration (FDA) regulations and International Conference on Harmonization (ICH) guidelines. The PI will carefully monitor each subject throughout the study for possible adverse events. All AEs will be documented on CRFs designed specifically for this purpose. It will be important to report all AEs, whether serious or non-serious.

11.3 Definitions of AEs & SAEs

11.3.1 Adverse Event

An adverse event (AE) is any unfavorable and unintended sign (including a clinically significant abnormal laboratory finding, for example), symptom, or disease temporally associated with a study, use of a drug product or device, whether or not considered related to the drug product or device.

Examples of adverse events include: new conditions, worsening of pre-existing conditions, clinically significant abnormal physical examination signs (i.e. skin rash, peripheral edema, etc.), or clinically significant abnormal test results (i.e. lab values or vital signs), with the exception of outcome measure results, which are not being recorded as adverse events in this trial (they are being collected, but analyzed separately). Stable chronic conditions (e.g. arthritis) that are present prior to the start of the study and do not worsen during the trial are NOT considered adverse events. Chronic conditions that occur more frequently (for intermittent conditions) or with greater severity are considered as worsened and therefore would be recorded as adverse events. Adverse events are generally detected in two ways:

- Clinical \rightarrow symptoms reported by the subject or signs detected on examination.
- Ancillary Tests → abnormalities of vital signs, laboratory tests, and other diagnostic procedures (other than the outcome measures, the results of which are not being captured as AEs).

If discernible at the time of completing the AE log, a specific disease or syndrome rather than individual associated signs and symptoms should be identified by the PI and recorded on the AE log. However, if an observed or

Randomized, Placebo-Controlled Parallel Group Clinical Trial of Nicotinamide Riboside to evaluate NAD+ Levels in Individuals with Persistent Cognitive and Physical Symptoms After COVID19 Illness ("Long-COVID")

Version 1.1

reported sign, symptom, or clinically significant laboratory anomaly is not considered by the PI to be a component of a specific disease or syndrome, then it should be recorded as a separate AE on the AE log. Clinically significant laboratory abnormalities, such as those that require intervention, are those that are identified as such by the PI.

Subjects will be monitored for AEs from the time they sign consent until completion of their participation in the study (defined as death, consent withdrawal, loss to follow up, early study termination for other reasons, or following completion of the entire study). An unexpected adverse event is any adverse event, the specificity or severity of which is not consistent with the current Investigator's Brochure.

The study procedures and the well-being of all participants will be monitored closely by the MGH principal investigator and the Co-Investigators. Throughout the course of the study, constant feedback with the subject is maintained in order to assess comfort and safety and to minimize risks throughout the procedure. The above investigators will be responsible for determining if a subject should be removed from the study. Criteria for removal include the following: 1) if a subject is unwilling or unable to participate in study procedures 2) if the subject refuses to participate and consent, 3) if the subject acquires a medical condition that prohibits further participation, 4) if in the opinion of the MGH principal investigator, [name], it is decided that it is not in the subject's best interest to continue participation.

Unanticipated problems including adverse events will be reported to the Partners Human Research Committee (PHRC) as described in the PHRC policy on Unanticipated Problems Involving Risks to Subjects or Others including adverse events.

The Data Management team will be responsible for the development, execution, and supervision of plans, policies, programs, and practices that control, protect, deliver, and enhance the value of data and information assets. All data will be managed in compliance with applicable regulatory requirements. The study coordinator, under the supervision of the PI, will collect, transcribe, correct, and transmit the data onto source documents, Case Report Forms (CRFs), and/or other forms used to report, track, and record clinical research data. The study coordinator will be instructed to enter this information into the REDCap database. The REDCap platform provides password protection. An edit checking and data clarification process will be put in place to ensure accuracy of the data. Logic and range checks as well as more sophisticated rules may be built into the eCRFs to provide immediate error checking of the data entered. The system has the capability to automatically create electronic queries for forms that contain data that are out of range, out of window, missing, or not calculated correctly. The platform will have the ability to lock specific visits to prevent any modification of data once the visit is closed. Once this option is activated, every user will have Read-Only access to the data. The PI, [name], will be responsible for ensuring the accuracy, completeness, legibility, and timeliness of the data reported.

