3.2.1 Standardized Cognitive, Functional, and Neuropsychiatric Outcome Measures

The primary outcome of this study will be objective measures of cognitive performance and subjective cognitive concerns measured with the following tests:

O The Mini-Mental State Examination (MMSE)²², Wechsler Adult Intelligence Scale-Fourth Edition (WAIS-IV) Digit Span backwards²³, Repeatable Battery for the Assessment of Neuropsychological Status (RBANS)²⁴, the Trail Making Test (TMT)²⁵, the Delis-Kaplan Executive Function System (DKEFS) Verbal Fluency²⁶, and the Continuous Performance Test (CPT). ²⁷ Subjective ratings of everyday cognitive functioning will be measured using items from the Behavior Rating Inventory of Executive Function (BRIEF-A)²⁸ at week 2, week 12 and week 22, and the Everyday Cognition scale (ECog)²⁹ will be measured at each visit.

The secondary and tertiary clinical and exploratory biomarker outcomes of this study will be:

• Assessment of neuropsychiatric symptoms as measured by:

Randomized, Placebo-Controlled Parallel Group Clinical Trial of Nicotinamide Riboside to evaluate NAD+ Levels in Individuals with Persistent Cognitive and Physical Symptoms After COVID19 Illness ("Long-COVID")

Version 1.1

- o Ratings of mood and anxiety will be measured using the Post Traumatic Stress Disorder Checklist-Civilian (PCL-C)³⁰, Beck Anxiety Inventory (BAI)³¹ and Beck Depression Inventory (BDI)³². These standard measures will be administered at each visit.
- Assessment of physical functioning as measured by:
 - o The Fatigue Severity Scale³³.
 - Objective daily physical activity levels and sleep data collected using wrist actigraphy (Fitbit Charge 4).
 - Subjective sleep ratings (Pittsburgh Sleep Quality Index)³⁴ and physical activity (International Physical Activity Questionnaire [IPAQ])³⁵ measures will be collected using questionnaires at each visit.
- Safety and tolerability will be assessed with adverse event (AE) reporting conducted at every visit.
- Plasma for biomarkers will be collected at Week 2, and at every 5 weeks until the end-of-study, and at the one-time visit for HC and long-covid participants. Plasma biomarkers assays will consist of ultrasensitive immunochemical measures of proteins reflecting neurodegeneration/neural injury (e.g. NfL, IL-6 and GFAP), as well as NAD+/NADH).
- Cerebral neurophysiology will be measured with functional MRI (optional sub-study).

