4.1.2 Exclusion Criteria

A subject will not be eligible for participation in the **clinical trial** if they meet any of the following criteria:

- 1. Any specific CNS disease history, such as major clinical stroke, brain tumor, normal pressure hydrocephalus, multiple sclerosis, delirium, significant head trauma with persistent neurological of cognitive deficits or complaints;
- 2. Clinically significant unstable medical condition that could affect safety or compliance with the study and would, in the opinion of the investigator, pose a risk to the participant if they were to participate in the study;
- 3. Was intubated due to COVID-19;
- 4. History of neuroimaging with evidence of major infarction, injury, infection, or other focal lesions that may be related to cognitive dysfunction;
- 5. Major active or chronic unstable psychiatric illness (e.g. depression, bipolar disorder, obsessive compulsive disorder, schizophrenia) within the previous year;
- 6. Current suicidal ideation;
- 7. History of alcohol or other substance abuse or dependence within the past two years;
- 8. Any significant systemic illness or medical condition that could affect safety or compliance with study;
- 9. Laboratory abnormalities in Vitamin B12, Thyroid Stimulating Hormone (TSH), or other common laboratory parameters that might contribute to cognitive dysfunction or other abnormalities in hematological, hepatic or renal function tests;

Randomized, Placebo-Controlled Parallel Group Clinical Trial of Nicotinamide Riboside to evaluate NAD+ Levels in Individuals with Persistent Cognitive and Physical Symptoms After COVID19 Illness ("Long-COVID")

Version 1.1

- 10. Current use of medications with psychoactive properties that in the opinion of the principal investigator, may be deleteriously affecting cognition (e.g., anticholinergics, antihistamines, antipsychotics, sedative hypnotics, anxiolytics);
- 11. Any known hypersensitivity to nicotinamide riboside, or its principal metabolite, nicotinamide mononucleotide;
- 12. No consumption of dietary supplements containing more than 100mg of niacin, nicotinamide riboside (NR), or nicotinamide mononucleotide (NMN) as the primary agents 30 days prior to baseline and for the duration of the trial.
- 13. Use of other investigational agents or interventions one month prior to entry and for the duration of the trial;

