9.1 Primary analysis

For all outcomes, we will perform intention-to-treat (ITT) analysis and mixed-effects model repeated measures (MMRM). Group (NR-NR vs. PBO-NR sequence), time, and group by time interactions will be included in the MMRM as fixed effects. The study's outcomes will be the change score of ECog, RBANS, and TMT-B from baseline, and the change in NAD+ levels from baseline. We also will examine changes in the FSS, BAI, BDI, and PSQI scores. An unstructured covariance matrix will be used to account for the correlation of repeated measures within a participant. Age, sex, and education will be included in the models as covariates.

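### Section 11.3.1 keeps outcome-measure results out of adverse event recording with no exception for BDI Question 9, and 10.1.1 does not say whether suicidality found that way is recorded as an AE or SAE

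*Combined protocol and SAP*

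**What the plan says.** Section 11.3.1 gives examples of adverse events and ends the list "with the exception of outcome measure results, which are not being recorded as adverse events in this trial". It adds that "they are being collected, but analyzed separately". Lower down, where detection is split into a clinical route and an ancillary-test route, the exclusion returns under ancillary tests: "other than the outcome measures, the results of which are not being captured as AEs". Neither statement is qualified.

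The BDI is an outcome measure. Section 3.2.1 lists it with the PCL-C and BAI among the neuropsychiatric outcomes and says "These standard measures will be administered at each visit". Section 9.1 includes it in the analysis: "We also will examine changes in the FSS, BAI, BDI, and PSQI scores".

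Section 10.1.1 (Other Risks) also makes the BDI a safety trigger: "A response of 2 or 3 on Question 9 of the BDI, or any spontaneous expression of suicidality will result in emergent evaluation". A response of 1 is treated as non-urgent, with clinician assessment and, if needed, triage within 48 hours. The section does not mention the AE log, severity, causality or seriousness. Sections 11.3 to 11.5 do not mention Question 9 or suicidality.

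Safety and tolerability is a stated outcome in 3.2.1, to be assessed through AE reporting at every visit.

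**The concern.** The protocol foresees a specific harm, names the instrument that will detect it and sets out an urgent response. The recording rule closest to that instrument says that its results are not adverse events. Staff who have just arranged an emergent evaluation are not told whether to open an AE entry.

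The credibility of the safety result is at stake. If such events are left out, or logged by some staff and not others, the AE tables could show little or no suicidality although the study had detected it and acted on it. With 60 participants in one arm and 40 in the other, a handful of unrecorded events could alter the safety comparison.

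**Working it through.** The plan states no figure on this point. The check is a cross-reading of the sections, followed by a simple count.

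**Reading the rules together**

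1. A BDI Question 9 response is an outcome-measure result (3.2.1, 9.1). Read literally, both exclusion statements in 11.3.1 apply to it.
2. The same response is also something the participant reports. The clinical route in 11.3.1 counts reported symptoms and examination signs as adverse events, and it carries no exclusion.
3. Section 11.3.1 does not say which reading governs when one answer fits both. Section 10.1.1 does not settle it.
4. Section 10.1.1 has two triggers for the same emergent evaluation: a Question 9 response of 2 or 3, and a spontaneous expression of suicidality. The second is not an outcome result, so the exclusion does not touch it. Two participants managed identically could therefore be recorded differently.
5. Serious adverse events are defined in 11.3.2 as adverse events meeting further criteria, and the 24-hour report in 11.5 applies to those. An event not accepted as an AE reaches neither step.

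**Whether the separate analysis recovers the event**

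Section 9.1 analyses change in BDI score and plans no count or listing of Question 9. Section 7.1.2.1.2 describes 21 items on a 0 to 3 scale. Assuming that the score is the sum of the items:

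- Maximum score: 21 x 3 = 63.
- Largest change from Question 9 alone: 3 points.
- Effect of one such change on a group mean: 3/60 = 0.05 points in the larger arm, 3/40 = 0.075 points in the smaller.

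A shift of that size cannot be seen in a comparison of mean change.

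**Count of administrations**

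Inputs: the neuropsychiatric row of the schedule in 6.1 marks Weeks 0, 2, 7, 12, 17 and 22, plus early discontinuation; 100 trial participants (3.1). All participants are assumed to attend every scheduled visit, so the counts are upper limits.

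- All scheduled visits: 6 x 100 = 600.
- Weeks 0 and 2 precede randomised treatment, so they are removed: 4 x 100 = 400.
- Within these, Weeks 7 and 12 cover the 10 weeks in which one arm takes placebo: 2 x 100 = 200.

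The documents give no rate for a response of 2 or 3. Over an assumed range of 0.5% to 2%:

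| Administrations | at 0.5% | at 2% |
|---|---|---|
| 400 (Weeks 7 to 22) | 400 x 0.005 = 2 | 400 x 0.02 = 8 |
| 200 (Weeks 7 and 12) | 200 x 0.005 = 1 | 200 x 0.02 = 4 |

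These are responses that could go unrecorded, not a forecast of losses. One person may respond positively more than once, and some responses may be logged through the clinical route.

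**The case against.** The strongest reply is that the exclusion attaches to test results and not to clinical conditions. In the AE examples it follows the item on abnormal test results, and its repeat sits under ancillary tests. New conditions, worsened conditions and reported symptoms all remain adverse events. A clinician who confirms ideation at the evaluation has a clinical finding that can be logged. Participants are also asked about problems or symptoms at each visit (11.4.1), and the hospitalisation and important-medical-event criteria in 11.3.2 could make such an event serious. Keeping efficacy scores out of AE listings is ordinary practice.

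Much of this stands. A reader might infer that 11.3.1 prohibits recording suicidality. It does not: the clinical route permits it. What the reply does not supply is an instruction. The visit question is general and does not name suicidality, the seriousness criteria apply only once something counts as an AE, and nothing says that a finding first raised by an outcome instrument leaves the exclusion.

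A reader might also infer that the BDI is the trial's sole scheduled check. The schedule in 6.1 marks an eligibility review at Weeks 0 to 22, and "Current suicidal ideation" is a trial exclusion in 4.1.2. The supported statement is that the BDI is the only named instrument. The review has no stated method, is missing from the follow-up visit list in 6.2.3, and concerns participation rather than event recording.

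Finally, a reader might extend the point to the cognitive decline anticipated in 10.1.1. The documents support that poorly: cognition is the primary outcome, and change in RBANS, TMT-B and ECog is analysed by group in 9.1, so a general worsening would appear there.

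**Conclusion.** The point holds as an ambiguity and a missing link. The exclusion is unqualified, the BDI falls within its wording, 10.1.1 does not connect Question 9 or the resulting evaluation to AE/SAE recording, and the change-score analysis would not show the event. Suicidality found through the BDI could be omitted or logged inconsistently.

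The size is up to 400 scheduled administrations after randomised treatment starts, or 2 to 8 responses at an assumed 0.5% to 2%. The rate is purely an assumption, and the conclusion does not depend on it, because the gap lies in the recording rule. The change is worth making because the rule bears on a stated outcome and narrowing it costs almost nothing.

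A related matter concerns participation. Section 5.4 discontinues a participant who newly meets any exclusion criterion, 4.1.2 lists current suicidal ideation as one, and 10.1.1 describes only assessment and triage. A reader might call this a contradiction. Both can apply to the same person, one as the immediate response and the other as the rule on continuing, so the documents support only that the sections need to be reconciled. This review takes no position on which rule should govern.

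**What to change.** - In both places in 11.3.1, limit the exclusion to outcome scores as such.
- State there that new or worsened suicidality identified through BDI Question 9, or at the clinician evaluation under 10.1.1, is entered in the AE log and assessed for severity, causality and seriousness under the existing rules. These include the rule that stable conditions present before the study are not adverse events. This does not require logging every response of 1.
- Add a cross-reference to that rule in 10.1.1.
- Reconcile 5.4, 4.1.2 and 10.1.1 on continued participation when suicidal ideation is newly detected.

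The cost is a few sentences of text and a few more AE log entries, so the AE table may look slightly less favourable. No new procedure is needed, because coordinators already review the relevant BDI answers during the visit.
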